10.2 Adverse events

TEAEs are defined as AEs which had onset on or after the first dose of IMP. AEs with an incomplete onset date will be classified as TEAEs if the month and year of onset (when only the month and year are specified) is the same as or after the month and year of the first dose of IMP or the year of onset (when only year is specified) is the same as or after the year of first dose of IMP.

AEs are classified by study period as described in Section 3.2.2.

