### Adverse events 11.1

### Definitions 11.1.1

### 11.1.1.1 Adverse event

urment to strict An AE is any untoward medical occurrence in a patient or clinical investigation subject administered a pharmaceutical product that does not necessarily have a causal relationship with this treatment. An AE can therefore be any unfavorable and unintended sign (including an abnormal laboratory finding), symptom, or disease temporally associated with the use of a medicinal (investigational) product, whether or not related to the medicinal (investigational) product.

In order to ensure complete safety data collection, all AEs occurring during the study (ie, after the signing of the Informed Consent form), including any pretreatment and posttreatment periods required by the protocol, must be reported in the eCRF even if no IMP was taken but specific study procedures were conducted. This includes all AEs not present prior to the initial visit and all AEs that recurred or worsened after the initial visit.

Signs or symptoms of the condition/disease for which the IMP is being studied should be recorded as AEs only if their nature changes considerably or their frequency or intensity increases in a clinically significant manner as compared to the clinical profile known to the Investigator from the subject's history or the Baseline Period.

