2.2.3 Primary safety variables

The primary safety variables are as follows:

- Incidence of treatment-emergent adverse events (TEAE)
- Incidence of TEAEs leading to study withdrawal
- Incidence of treatment-emergent serious adverse events (SAEs)

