2.3.1 Study duration per subject

study or M' t whr Aside from the Open-Label Temporary Period, the total duration of the study will be up to approximately 26 weeks with a maximum 16-weeks exposure to BRV consisting of the following study periods:

- Baseline Period (8 weeks)
- Treatment Period (12 weeks)
- Down-Titration Period (4 weeks) .
- Study Drug-Free Period (2 weeks)
- Transition Period (2 weeks) (required for subjects participating in the LTFU study or MAP)
- Open-Label Temporary Period (for subjects who are assigned to enter MAP but who cannot directly convert to MAP; starts after the end date of the Transition Period and continues until date when subject can convert to MAP, BRV is commercially available or until UCB decides to close the study)

A schematic diagram of study periods is shown in Figure 2-1

Figure 2-1 Schematic diagram of study periods

Ideally, visits should occur on the specified Visit/Week. A ±3 days window for each specified Visit/Week is allowed, provided the subject has adequate investigational medicinal product (IMP) to sustain the visit window.

The end of the study is defined as the date of the last visit of the last subject in the study.

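### SAP 10.2 has no end-date check for AEs with incomplete onset dates, so a Baseline AE known to have ended before the first dose can be counted as a TEAE

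*SAP*

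**What the plan says.** SAP 10.2 gives the definition first: "TEAEs are defined as AEs which had onset on or after the first dose of IMP". The next sentence covers partial dates. AEs with an "incomplete onset date will be classified as TEAEs if the month and year of onset" are the same as or later than those of the first dose are TEAEs. When the month is also missing, the test is whether "the year of onset (when only year is specified) is the same as or after the year of first dose of IMP". Neither branch has a condition on the end date.

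The section then adds that "AEs are classified by study period as described in Section 3.2.2". SAP 3.2.2 sets period boundaries by visit dates and has no rule for partial dates. SAP 10.2.1 and Protocol 13.4.1 contain no exception either.

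AEs that started and ended before dosing are within the data collected. Protocol 11.1.1.1 requires reporting of "all AEs occurring during the study (ie, after the signing of the Informed Consent form), including any pretreatment and posttreatment periods", and SAP 2.3.1 gives an 8-week Baseline Period. Protocol section 9 has the daily record card capture start and end dates of undesirable events. SAP 2.2.3 makes the incidence of TEAEs and of treatment-emergent SAEs primary safety variables.

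**The concern.** An event that ended before the first dose cannot have started on or after it. For a record with an incomplete onset date and such an end date, the partial-date sentence therefore contradicts the definition just before it.

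The SAP already uses this kind of test elsewhere: section 6.5 defines prior medication by an end date before the first administration. SAP 10.2.1 also treats pre-treatment AEs as a separate category that is only listed.

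What is at stake is the count in a primary safety variable. Two further rules in SAP 10.2.1 can add to a single error:

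- Unspecified intensity is taken as severe and unspecified relationship as drug-related. A resolved Baseline event with those fields blank would be tabulated as a severe, drug-related TEAE.
- One table uses a threshold of 2% of subjects in any group. With 148 per arm, 3 subjects is 3/148 = 2.03% and 2 subjects is 2/148 = 1.35%, so one misclassified subject could bring a term into the table.

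**Working it through.** The documents state no figure on this point, so there is none to reproduce.

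**Step 1. Apply the rule to test records, first dose 20 June 2020.**

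| Onset recorded | End recorded | SAP 10.2 | With end-date check |
|---|---|---|---|
| June 2020 | 10 June 2020 | TEAE | not TEAE |
| 2020 | 15 May 2020 | TEAE | not TEAE |
| 5 June 2020 | 10 June 2020 | not TEAE | not TEAE |
| May 2020 | 20 May 2020 | not TEAE | not TEAE |

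Only the first two rows go wrong. The third shows that complete dates are handled correctly. The fourth shows that a partial date in a month before the first dose is too.

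**Step 2. Upper bound on reach.** Inputs: a 56-day Baseline (8 weeks, SAP 2.3.1). Assumed: onset uniform over those days, first-dose dates uniform over a 365-day year.

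- *Day missing.* With the first dose on day D of a month, D − 1 Baseline days share that month. Over the year the mean is [7×(31×30/2) + 4×(30×29/2) + 28×27/2]/365 = 5373/365 = 14.72 days, and 14.72/56 = 0.263.
- *Month missing.* Baseline days fall in the previous year only when dosing is in the first 56 days of the year. Total loss is 56 + 55 + … + 1 = 1596 days, so the share is 1 − 1596/(365×56) = 0.922.

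With the ±3-day visit windows, taken as a Baseline of 50 to 62 days, these become 29% to 24% and 93% to 91%. They cover all partial-date Baseline AEs that the rule calls TEAEs, including those whose end date leaves onset on treatment possible.

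**Step 3. The part that is actually wrong.** Assume also that each AE ends 7 days after onset with a usable end date. It is then over before dosing if onset was at least 8 days earlier.

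- *Day missing.* [7×(23×24/2) + 4×(22×23/2) + 20×21/2]/365 = 3154/365 = 8.64 days, and 8.64/56 = 0.154.
- *Month missing.* 49 of the 56 days qualify, less a year-boundary loss of (8×49 + 48 + 47 + … + 1)/365 = 1568/365 = 4.30. Then (49 − 4.30)/56 = 0.798.

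**Step 4. Illustrative count in 444 subjects.** Count = 444 × b × p × s × r, where b is the proportion of subjects with one Baseline AE (assumed 10% to 30%), p the proportion of those AEs with an incomplete onset date (assumed 1% to 10%), s the share from Step 2, and r the proportion of these provably resolved before dosing (assumed 50% to 80%).

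- *All day-missing:* 444×0.1×0.01×0.263×0.5 = 0.06, up to 444×0.3×0.1×0.263×0.8 = 2.8.
- *All month-missing:* 444×0.1×0.01×0.922×0.5 = 0.2, up to 444×0.3×0.1×0.922×0.8 = 9.8.

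The 7-day case implies r = 0.154/0.263 = 0.59 for day-missing records, inside the assumed range. For month-missing records it implies 0.798/0.922 = 0.87, slightly above it.

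**Step 5. Effect on arms.** If a fraction e of subjects without a true TEAE gains a false one, incidence t becomes t + (1 − t)e, and a difference between arms is multiplied by 1 − e. The worst day-missing count gives at most 2.8/444 = 0.6%. Taking e = 1% and assumed incidences of 55% and 65%: 0.55 + 0.45×0.01 = 55.45% and 0.65 + 0.35×0.01 = 65.35%. The difference moves from 10.0 to 9.9 points.

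**The case against.** The best case against is that almost no record can meet the conditions. An error needs a Baseline AE, an incomplete onset date, and an end date good enough to prove resolution before dosing. Subjects complete a card daily, and it is reviewed at visits about four weeks apart in Baseline (Protocol section 9, Table 5–1). Discrepancy checks and query resolution follow (Protocol 12.3.2, 13.5). A year-only onset is especially unlikely for an event arising within eight weeks of consent. This stands, and it is why the count is probably near zero.

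It can also be said that the rule is a deliberate worst-case convention, in line with how missing intensity and relationship are handled. That is a good defence when timing is unknown. It does not cover records whose end date settles the timing.

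A third argument is that SAP 10.2.1 limits its SOC and preferred-term tables to periods after Baseline, so these events would drop out. The text does not settle this. SAP 3.2.2 gives no way to place a partial-date AE in a period, and the overall TEAE summary carries no explicit period limit.

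Stronger readings are tempting but unsupported:

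- A reader might infer that Baseline AEs resolved before dosing are counted in general. They are not. Complete onset dates are classed correctly.
- A reader might take 26% and 92% as error rates. They include events whose onset could have been on treatment, which should stay TEAEs, and the 92% describes a record type that is unlikely to occur.
- A reader might infer a distorted BRV–placebo comparison. AE analysis is descriptive, with no planned between-arm test. The events precede treatment under 1:1:1 randomisation, so no arm is favoured in expectation.

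**Conclusion.** The point holds in a narrow form. For a Baseline AE with an incomplete onset date in the same month or year as the first dose, and a recorded end before that dose, SAP 10.2 gives a classification that contradicts its own TEAE definition. No other section corrects it.

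The number affected cannot be found from the documents and is probably near zero. The range of 0.06 to 2.8 AEs for day-missing records rests wholly on assumed Baseline AE, partial-date and resolution rates. The month-missing range, up to 9.8, also needs every incomplete date to lack its month. The expected effect is a slight inflation of absolute TEAE incidence in all arms. Efficacy and sample size are untouched. The matter is worth correcting because a stated rule misclassifies a primary safety variable, but its priority is low.

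**What to change.** Add to SAP 10.2: *An AE with an incomplete onset date is not treatment-emergent if its end date (complete, or partial but sufficient) is before the date of first dose of IMP.* Keep the present rule for every other incomplete onset date, including cases where the end date is missing, too incomplete to decide, or on or after the date of first dose.

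The cost is one sentence and one programming condition on dates the study already collects. No new data are needed.

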10.2.1 General summaries of AEs

An overall summary of TEAEs will provide the overall number of TEAEs and the numbers and percentages of subjects with at least 1 TEAE, with a TEAE that led to permanent discontinuation of study drug, with a TEAE leading to withdrawal from study, with a TEAE requiring dose change, with a drug-related TEAE, with a severe TEAE, and with a treatment-emergent serious
AE (SAE). The number and percentage of subjects who died due to AE as well as TEAE will also be summarized.

The following summaries of TEAEs will be provided by primary SOC and PT. All summaries are for all study periods combined excluding Open-Label Temporary period (Treatment, Down-Titration, Study Drug-Free Period, and Transition) unless otherwise indicated. Summaries for Open-Label Temporary will be presented separately. The number of individual occurrences will be included with the numbers and percentages if applicable.

- Incidence of TEAEs
- Incidence of TEAEs by study period (Treatment, Down-Titration, Study Drug-Free, and Transition Periods)
- Incidence of drug-related TEAEs by study period (Treatment, Down-Titration, Study Drug-Free, and Transition Periods)
- Incidence of TEAEs occurring in at least 2% of subjects in any treatment group
- Incidence of TEAEs occurring in at least 2% of subjects by relationship to study drug in any treatment group
- Incidence of non-serious TEAEs occurring in at least 5% of subjects in any treatment group
- Incidence of non-serious TEAEs occurring in at least 5% of subjects by relationship to study drug in any treatment group
- Incidence of TEAEs by intensity
- Incidence of TEAEs by maximum intensity
- Incidence of TEAEs by relationship to study drug
- Incidence of TEAEs by maximum relationship to study drug
- Incidence of treatment-emergent SAEs
- Incidence of non-serious TEAEs
- Incidence of TEAEs leading to permanent discontinuation of study drug
- Incidence of TEAEs leading to discontinuation of study
- Incidence of TEAEs related to COVID-19 vaccination by study period

For the summary by maximum intensity and by maximum relationship, each subject will be counted at most once per primary SOC or PT according to the maximum intensity and the maximum relationship of all AEs within that SOC or PT. For the summary by intensity and by relationship, a subject may be counted more than once according to the intensity of the TEAEs and the relationship assessments.

Severe intensity will be assumed for AEs for which intensity is not specified.

Drug-related TEAEs are TEAEs for which the relationship to IMP is specified as Related or AEs for which relationship is not specified.

In addition, AEs including Pre-treatment AEs will be listed with respect to general information, relationship, seriousness, withdrawal of study drug and study discontinuation.

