### Study description 5.1

This is a randomized, double-blind, PBO-controlled, multicenter, therapeutic confirmatory study evaluating 2 doses of BRV. The subject population will be subjects ( $\geq 16$  to 80 years of age) with partial seizures with or without secondary generalization. Subjects who are not legal adults will be included only where legally permitted and ethically accepted. Subjects will complete an 8week prospective Baseline Period, followed by a 12-week Treatment Period.

Subjects may be eligible for conversion to a LTFU study or MAP upon completion of the Treatment and Transition Period. There is a 4-week Down-Titration Period followed by a 2-week Study Drug-Free Period for subjects not entering the LTFU study or MAP. If BRV is commercially available upon subject completion of the Treatment and Transition Period, subjects will receive BRV directly without entering the LTFU study or MAP.

A 1:1:1 central randomization (random permuted blocks) stratified for country, LEV use (LEV naïve vs prior LEV use), and number of AEDs previously used but discontinued prior to study entry ( $\leq 2 \text{ vs} \geq 2 \text{ AEDs}$ ) will be used to ensure the balance across treatment groups (PBO, BRV 50mg/day, BRV 200mg/day) within each combination of stratification levels. Randomization

will not be stratified by study center due to the expected small number of randomized subjects per study center.

No restrictions are placed on the proportion of randomized subjects within each stratification level, either overall or on a regional basis.

The total duration of the study will be up to approximately 26 weeks with a maximum 16-weeks exposure to BRV consisting of the following study periods: Baseline Period (8 weeks) eting authori FU stud

- Treatment Period (12 weeks) ٠
- Down-Titration Period (4 weeks) •
- Study Drug-Free Period (2 weeks)
- Transition Period (2 weeks) (required for subjects participating in the LTFU study or MAP)

Ideally, visits should occur on the specified Visit/Week. A  $\pm 3$  day window for each specified Visit/Week is allowed, provided the subject has adequate investigational medicinal product (IMP) to sustain the visit window.

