- For the subject who has completed the Treatment Period, the Investigator will decide whether the subject would benefit or not from continuing the treatment with BRV at the end of the Treatment Period (Visit 7). If the investigator decides the subject would benefit from continued BRV treatment and the subject desires to continue treatment, the subject will enter the LTFU study or MAP.
- Prior to entry into LTFU study or MAP, the informed consent, where applicable, should be obtained from the subject at the end of Treatment Period (Visit 7). Subsequently, the subject will go through the Transition Period, and will be dosed in a double-blind manner in order to maintain the blind.
- As a procedure of MAP, the import license of medication for MAP is necessary. The process to obtain the import license starts after patient enrollment and can on occasions take a long time. To avoid a scenario where a subject cannot enter MAP due to the delayed importation of medication, a temporary period for providing BRV will be prepared as the rescue. Once medication for MAP is ready, a subject can start MAP.

The end of the study is defined as the date of the last visit of the last subject in the study.

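### Serious TEAEs, TEAEs leading to discontinuation, intensity and the 2%/5% tables are given only as crude percentages over all periods combined, and the length of that window depends on a path taken after randomization

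*SAP*

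**What the plan says.** SAP 10.2.1 sets the default window for the TEAE tables by SOC and PT: "All summaries are for all study periods combined excluding Open-Label Temporary period", unless a table is marked otherwise. The periods pooled are Treatment, Down-Titration, Study Drug-Free and Transition. Three tables are marked by study period: all TEAEs, drug-related TEAEs, and TEAEs related to COVID-19 vaccination. The tables for treatment-emergent SAEs, TEAEs leading to discontinuation of study drug or of study, intensity, and the 2% and 5% cut-offs are not. The statistics are numbers and percentages of subjects and, where applicable, numbers of occurrences.

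The TEAE definition in SAP 10.2 has a start (first dose) but no end. SAP 10.1 describes exposure duration but does not link it to AE rates.

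What follows Week 12 is decided after randomization. Protocol 5.1 says that at Visit 7 "the Investigator will decide whether the subject would benefit or not from continuing the treatment with BRV". Those who continue pass through a 2-week Transition Period. For the rest, "There is a 4-week Down-Titration Period followed by a 2-week Study Drug-Free Period for subjects not entering the LTFU study or MAP".

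SAP 2.2.3 names three primary safety variables: incidence of TEAEs, of TEAEs leading to study withdrawal, and of treatment-emergent SAEs.

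**The concern.** Two of the three primary safety variables, SAEs and TEAEs leading to withdrawal, have no planned TEAE table over a window common to all arms. Their only window is the pooled one, and its length is set by a choice that follows perceived benefit. Response and tolerability may differ by arm, so the mix of paths may too. An arm with more scheduled follow-up would then accumulate more subjects with at least one event, even at identical risk.

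A second, smaller issue concerns the by-period tables. They put crude percentages side by side for periods of 12, 4, 2 and 2 weeks. A reader who compares across periods is comparing different lengths of observation.

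**Working it through.** **Plan's own figures.** SAP 2.3.1 lists Baseline 8, Treatment 12, Down-Titration 4, Study Drug-Free 2 and Transition 2 weeks. It states about 26 weeks in total and at most 16 weeks of BRV exposure. Check: 8 + 12 + 4 + 2 = 26 and 12 + 4 = 16. Both reproduce. The 26 weeks describe the Down-Titration path.

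**Scheduled follow-up after first dose, by path**

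| Path | Source | Weeks |
|---|---|---|
| Transition, then LTFU, MAP or commercial BRV | SAP 2.3, 2.3.1 | 12 + 2 = 14 |
| Down-Titration, then Study Drug-Free | SAP 2.3 | 12 + 4 + 2 = 18 |
| Transition, then Down-Titration and Study Drug-Free | SAP 3.2.2 | 12 + 2 + 4 + 2 = 20 |
| Early discontinuation | Protocol, asterisked note after the Table 5–1 footnotes | time to EDV + 4 + 2 |

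An early discontinuer has fewer than 14 weeks if the EDV falls before Week 8, since 8 + 6 = 14.

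**Illustration.** The documents give no event rates and no entry shares, so both are assumptions here. With a constant hazard equal in all arms and periods:

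- h = −ln(1 − p12)/12, where p12 is the 12-week incidence
- F(t) = 1 − exp(−h·t)
- pooled arm percentage = s·F(14) + (1 − s)·F(18), where s is the share entering LTFU or MAP (only the first two paths)
- gap between arms = (difference in s) × [F(18) − F(14)]

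*TEAEs, p12 = 60%.* h = 0.0764 per week, F(14) = 65.7%, F(18) = 74.7%, a difference of 9.0 points.

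- 95% versus 85% entry: 0.10 × 9.0 = 0.9 points
- 95% versus 75%: 0.20 × 9.0 = 1.8 points
- 90% versus 60%: 0.30 × 9.0 = 2.7 points

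For 95% versus 85% entry, other values of p12 give 0.74 points (30%), 0.92 (50%) and 0.81 (70%). With equal shares the gap is zero.

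*SAEs, p12 = 3%.* F(14) = 3.49% and F(18) = 4.47%.

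- 90% entry: 0.9 × 3.49 + 0.1 × 4.47 = 3.59%
- 60% entry: 0.6 × 3.49 + 0.4 × 4.47 = 3.88%
- gap 0.29 points, ratio 0.92. At 148 per arm this is about 0.4 of a subject.

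*By period, p12 = 60%.* The same constant risk prints as 60% for Treatment (12 weeks), F(4) = 26% for Down-Titration, and F(2) = 14% for Transition or Study Drug-Free.

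**The case against.** The strongest reply is that the plan already covers the main comparison. The by-period tables for all TEAEs and drug-related TEAEs have a Treatment Period part, which compares the arms over the same scheduled 12 weeks. A reader might infer that every AE arm contrast in the plan moves with follow-up time. The documents do not support that: the problem is confined to tables with no by-period version. Also, SAP 5.1.1 tabulates Treatment Period discontinuations by primary reason and adds a table of discontinuations due to AEs. These help with withdrawals, but they are not TEAE tables by SOC and PT, and they do nothing for SAEs or intensity.

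A reader might also infer that pooling makes BRV look safer, because placebo subjects would more often decline continuation and be followed for 18 weeks. That direction is not established. If low LTFU/MAP entry in an arm reflects early dropout, the shift can reverse. Under the 60% assumption, a subject with an EDV at Week 4 is followed for 4 + 6 = 10 weeks and has F(10) = 53%, below the 65.7% of a subject followed for 14 weeks. Transition dosing is also double-blind and open to the placebo arm, so a large difference in entry is only a supposition.

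The size is modest. The TEAE shifts above compare with a standard error of about 5.4 points for a difference at 148 per arm. The model also applies the Treatment Period hazard to taper and drug-free weeks, although under Protocol 7.2 the 50 mg/day arm takes placebo for 3 of the 4 down-titration weeks.

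Finally, the safety tables are descriptive, no comparison between periods is planned, and pooling keeps taper and post-drug events in view. That is a good reason to keep the all-periods tables. It is not a reason to have no common-window table for SAEs.

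**Conclusion.** The point holds in a limited form. Serious TEAEs, TEAEs leading to discontinuation, intensity and the 2%/5% tables are reported only as crude percentages over a window of 14, 18, 20 or EDV-plus-6 weeks, according to a path taken after randomization. If the path mix differs by arm, those contrasts shift with no true difference. The direction cannot be known from the documents.

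The illustrative size is about 0.9 points per 10-point difference in LTFU/MAP entry for TEAEs, and about 0.3 points for SAEs at 90% versus 60% entry. Both rest on assumed shares, assumed rates and a constant hazard. All TEAEs and drug-related TEAEs already have a sound Treatment Period comparison, early discontinuation aside. Percentages across periods of different length are not comparable with one another. This is a cheap improvement, not a defect that threatens the safety conclusions.

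**What to change.** In SAP 10.2.1, add tables restricted to the Treatment Period (Visit 3 to Visit 7/EDV, as defined in SAP 3.2.2) for treatment-emergent SAEs, TEAEs leading to discontinuation, and maximum intensity. Place them alongside the all-periods tables, which stay as planned.

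To the Treatment Period, by-period and all-periods tables, add subject-time of follow-up and incidence per 100 subject-weeks by arm. The rates are needed even in the Treatment Period tables, because that window ends at the EDV for early discontinuers.

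The cost is a few more tables and one follow-up-time variable. AEs are already classified by study period (SAP 10.2), and the period dates are already defined.
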